dose is recovered in urine and feces as unchanged parent drug. The mean terminal elimination half-life ($T_{1/2}$) is ~ 3 h with no appreciable accumulation of either parent or metabolites with twice daily dosing. Metabolism is predominantly via the cytochrome P450 isozyme, family 3, subfamily A (CYP3A4) to yield oxygenated and subsequent conjugated metabolites. Oxidative metabolites of ruxolitinib retain pharmacological activity albeit with 0.5 to 0.2 of the activity of the parent compound. Ex vivo pharmacokinetic/pharmacodynamic (PD) analysis indicates that the total of 8 active metabolites contribute to 18% of the overall pharmacodynamic activity of ruxolitinib. When administering ruxolitinib with strong CYP3A4 inhibitors, the total daily dose should be reduced by approximately 50%. No dose adjustment is necessary when co-administering ruxolitinib with strong CYP3A4 inducers. No dose adjustment is necessary when co-administering ruxolitinib with CYP3A4 substrates. Ruxolitinib did not decrease the exposure of a fixed dose oral contraceptive metabolized via the CYP3A4 pathway, thus demonstrating lack of CYP3A4 induction potential.

In subjects with severe renal impairment (creatinine clearance (CLcr) < 30 mL/min), the dose based on platelet count should be reduced by approximately 50% to be administered twice a day. Ruxolitinib doses should be titrated based on individual safety and efficacy.

In subjects with mild, moderate or severe hepatic impairment, the recommended starting dose based on platelet count should be reduced by approximately 50% with subsequent dose titration based on individual safety and efficacy.

Ruxolitinib PK in healthy volunteers was largely comparable between Japanese, Chinese and Western subjects and studies led to a conclusion of no meaningful ethnic differences in exposure.

A thorough QT study was conducted in 50 healthy subjects. There was no indication of a QT/corrected QT interval (QTc) prolonging effect of ruxolitinib in single doses up to a supratherapeutic dose of 200 mg indicating that ruxolitinib has no effect on cardiac repolarization.

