* Note: If total bilirubin > 3.0 x ULN is due to the indirect (non-conjugated) component only, and hemolysis as the etiology has been ruled out as per institutional guidelines (e.g., review of peripheral blood smear and haptoglobin determination), then reduce 1 dose level and continue treatment at the discretion of the Investigator.	
** Note: A CT scan or other imaging study to assess the pancreas, liver, and gallbladder must be performed within 1 week of the first occurrence of any ≥ Grade 3 of amylase and/or lipase. If asymptomatic Grade 2 elevations of lipase and/or amylase occur again at the reduced dose, subjects will be discontinued permanently from study treatment.	
*** Note: antidiarrheal medication is recommended at the first sign of abdominal cramping, loose stools or overt diarrhea	

Table 6-4 Dose reduction steps for ruxolitinib

Dose Reduction steps of ruxolitinib *			
Groups	Starting dose level – 0	Dose level – 1	Dose level – 2
Group 1	10 mg BID	5 mg BID	5 mg QD**
Group 2	5mg BID	5 mg QD or 2.5mg BID	Not applicable

Dose Reduction steps of ruxolitinib *			
Group 3	4 mg/m ² BID	50% of starting dose BID	Not applicable
Group 4	Starting dose BID***	50% of starting dose BID	Not applicable
*Dose reduction should be based on the worst toxicity demonstrated at the last dose.			
**Dose reduction below 5 mg total daily dose is not allowed.			
***Based on prior data collected from [CINC424F12201] and [CINC424C2301], [CINC424D2301].			

Subjects who have had a dose reduction of ruxolitinib in order to manage toxicity may resume treatment at the previous dose if hematologic/non-hematologic parameters meet the required threshold(s).

Table 6-5 Dose re-escalation levels for ruxolitinib

Dose Re-escalation*			
	Current dose	First dose escalation	Second dose escalation
Group 1	5 mg QD	5 mg BID	10 mg BID
	5 mg BID	10 mg BID	*
Group 2	5mg QD or 2.5 mg BID	5mg BID	Not applicable
Group 3	50% of starting dose BID	Starting dose BID	Not applicable
Group 4	50% of starting dose BID	Starting dose BID	Not applicable

Except for Group 1, all other dose escalations are examples and may not reflect the actual starting dose.
*Dose increases may not exceed 10 mg BID, in increments of 5 mg and not more often than every 2 weeks.

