6.5.1.3 Dose modification for ruxolitinib when combined with CYP450 modulators

In all cases when ruxolitinib is co-administered with CYP450 modulators, subjects should be closely monitored and dose titrated based on safety (see [Section 6.5.1.2](#)).

See [Section 16.7](#) for a list of CYP3A4 inhibitors and inducers.

Strong CYP3A4 inhibitors

A dose reduction of ruxolitinib (e.g. by 50%) should be considered when using strong CYP3A4 inhibitors. No dose adjustment of ruxolitinib is needed for use with topical ketoconazole. See [Section 6.5.1.2](#)

Mild or moderate CYP3A4 inhibitors

No dose adjustment is recommended when ruxolitinib is co-administered with mild or moderate CYP3A4 inhibitors.

Dual CYP2C9 and CYP3A4 inhibitors

A dose reduction of ruxolitinib (e.g. by 50%) must be considered when using medicinal products which are dual inhibitors of CYP2C9 and CYP3A4 enzymes (e.g. fluconazole). Avoid the concomitant use of ruxolitinib with fluconazole doses greater than 6 mg/kg (maximum 200 mg) daily.

CYP3A4 inducers

No dose adjustment is recommended when ruxolitinib is co-administered with CYP3A4 inducers.

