12.5.3 Pharmacokinetics

Pharmacokinetic analysis set (PAS) will be used in all pharmacokinetic data analysis and PK summary statistics.

Pharmacokinetic variables:

Ruxolitinib concentration sparse profiles will be summarized by time point. Pharmacokinetic parameters, e.g. AUC0-12h and Cmax and Ctrough, will be determined using Population PK method(s) for ruxolitinib, and methods detailed in an independent analysis plan.

Statistical methods for pharmacokinetic analyses

Ruxolitinib concentrations data will be listed by age group and formulation. Descriptive summary statistics will be provided by age group/formulation at each scheduled time point. Summary statistics will include n (number of subjects with non-missing values), mean (arithmetic and geometric), standard deviation (SD), coefficient of variation (CV%) (arithmetic and geometric), median, minimum and maximum. Individual profiles with median by age group/formulation as well as arithmetic mean with SD and geometric mean ruxolitinib plasma concentration versus time profiles by treatment will be displayed graphically.

Ruxolitinib plasma PK parameters data will be listed by age group/formulation. Descriptive statistics (n, arithmetic mean, SD, CV% for mean, geometric mean, geometric CV%, median, minimum and maximum) will be provided for all PK parameters by age group/formulation.

Population PK approach Concentration results from the sparse sampling will be analyzed using nonlinear mixed effects modeling (population PK) or other model-based approaches, as appropriate, and key pharmacokinetic parameters will be derived for the study population from sparse concentration-time data e.g. AUC, Cmax, Ctrough. Details of the analysis method will be developed in an independent PK analysis plan and the population PK analysis will be documented in a separate report.

During modeling of the pharmacokinetics of study treatment, the broad principles outlined in the Food and Drug Administration (FDA) guidance will be followed (Guidance for Industry: Population Pharmacokinetics; fda.gov/cder/guidance/1852fnl.pdf).

Exposure-Response analysis

A detailed description of exposure-response analysis will be developed in an independent analysis plan, and the analysis will be documented in a separate report. Briefly, the objectives are to:

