1.2 Study objectives and endpoints

Objectives and related endpoints are described in [Table 1-1](#) below.

Table 1-1 Objectives and related endpoints

Objective(s)	Endpoint(s)	Analysis	Analysis incl. in final CSR
Primary objective(s)	Endpoint(s) for primary objective(s)	Primary Analysis	

To evaluate the activity of ruxolitinib added to standard dose corticosteroids +/- CNI in pediatric subjects with moderate or severe treatment naive-cGvHD or SR-cGvHD measured by overall response rate (ORR) at Cycle 7 Day 1 based on all subjects in the study.	
Overall response rate (ORR) at Cycle 7 Day 1, defined as the proportion of subjects demonstrating a complete response (CR) or partial response (PR) without the requirement of additional systemic therapies for an earlier progression, mixed response or non-response. The response is assessed per NIH consensus criteria (Lee et al 2015), and scoring of response will be relative to the organ stage at the start of study treatment.	
Refer to Section 2.5.1	No
Secondary objective(s)	Endpoint(s) for secondary objective(s)	Secondary analysis	

To assess pharmacokinetics (PK) of ruxolitinib in treatment-	
Ruxolitinib concentrations by timepoint	
Refer to Section 2.9	No

Objective(s)	Endpoint(s)	Analysis	Analysis incl. in final CSR
naïve cGvHD and SR-cGvHD pediatric subjects			
• To evaluate the safety of ruxolitinib	• Safety and tolerability will be assessed by monitoring the frequency, duration and severity of Adverse Events, including occurrence of any second primary malignancies or infections, and by performing physical exams and evaluating changes in vital signs, tanner stage, chemistry and hematology results from baseline.	• Refer to Section 2.8	Yes
• To assess duration of response (DOR)	• Duration of response (DOR) is assessed for responders only. DOR is defined as the time from first response until cGvHD progression, death, or the date of addition of systemic therapies for cGvHD.	• Refer to Section 2.7.2	Yes
• To estimate ORR at end of Cycle 3	• Proportion of subjects who achieve OR (CR+PR) at Cycle 4 Day 1		No

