2.2 Analysis sets

If the starting dose is different from the assigned dose level due to co-administration of ruxolitinib with strong CYP3A4/CYP2C9 inhibitors, these subjects will be included under the assigned dose level and considered that they have received the full assigned dose. This applies to Full Analysis Set, Safety Set, and Pharmacokinetic analysis set as described below.

If the treatment formulation (tablet/liquid) changed during treatment, the subject will be considered under the formulation she/he started treatment. Nevertheless, a change in formulation will be flagged and may be considered for PK analyses.

The **Full Analysis Set** (FAS) comprises all subjects to whom study treatment has been assigned and who received at least one dose of study treatment.

The **Safety Set** includes all subjects who received at least one dose of study treatment. Subjects will be analyzed according to the study treatment received, where treatment received is defined as the assigned dose level of ruxolitinib if the subject took at least one dose of that treatment or the first dose level received if the assigned dose level was never received.

The **Pharmacokinetic analysis set** (PAS) includes all subjects who provide at least one evaluable PK concentration. For a concentration to be evaluable, subjects are required to:

- Take the dose of ruxolitinib prior to PK sample

- For post-dose samples on Cycle 1 Day 1: do not vomit within 2 hours after the dosing of ruxolitinib
- For pre-dose samples: have the sample collected before the next dose administration of ruxolitinib; do not vomit within 2 hours after the previous dosing of ruxolitinib prior to sampling.

The **Listing only Set** contains only those patients who are not eligible for efficacy analyses due to PD “Patient enrolled and treated beyond local regulatory requirements”. These patients will also not be included in safety summary analyses, but all safety data will be provided in listings, separately from the listings of all other patients.

Patient Classification:

Patients may be excluded from the analysis populations defined above based on the protocol deviations entered in the database and/or on specific patient classification rules defined in [Table 2-3](#).

Patients with protocol deviation OTH12 “Patient enrolled and treated beyond local regulatory requirements” will only be included in the “Listing only Set” and not in any other analysis set.

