2.9 Pharmacokinetic endpoints

Analyses of PK data will not be repeated for the final CSR, since no PK samples were collected since interim CSR analyses..

Pharmacokinetic analysis set (PAS) will be used in all pharmacokinetic data analysis and PK summary statistics.

Pharmacokinetic variables:

Ruxolitinib concentration sparse profiles will be summarized by time point. Pharmacokinetic parameters, e.g. AUC0-12h and Cmax and Ctrough, may be determined using Population PK method(s) for ruxolitinib, and methods detailed in an independent analysis plan.

Statistical methods for pharmacokinetic analyses

Ruxolitinib concentrations data will be listed by Age group and formulation. Descriptive summary statistics will be provided by Age group/formulation at each scheduled time point. Summary statistics will include n (number of subjects with non-missing values), mean (arithmetic and geometric), standard deviation (SD), coefficient of variation (CV%) (arithmetic and geometric), median, minimum and maximum. Individual profiles with median by Age group/formulation as well as arithmetic mean with SD and geometric mean ruxolitinib plasma concentration versus time profiles by treatment will be displayed graphically.

Ruxolitinib plasma PK parameters data will be listed by Age group/formulation. Descriptive statistics (n, arithmetic mean, SD, CV% for mean, geometric mean, geometric CV%, median, minimum and maximum) will be provided for all PK parameters by Age group/formulation.

Population PK approach Concentration results from the sparse sampling will be analyzed using nonlinear mixed effects modeling (population PK) or other model-based approaches, as appropriate, and key pharmacokinetic parameters may be derived for the study population from sparse concentration-time data e.g. AUC, Cmax, Ctrough. Details of the analysis method will be developed in an independent PK analysis plan and the population PK analysis will be documented in a separate report.

During modeling of the pharmacokinetics of study treatment, the broad principles outlined in the Food and Drug Administration (FDA) guidance will be followed (Guidance for Industry: Population Pharmacokinetics; fda.gov/cder/guidance/1852fnl.pdf).

Data handling principles

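### Within each age group and formulation, the concentration summaries mix actual doses, dosing frequencies and CYP-inhibitor use, and a CYP-reduced starting dose in the PK set is labelled as the full assigned dose

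*SAP*

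**What the plan says.** The PK secondary endpoint in SAP 1.2 is "Ruxolitinib concentrations by timepoint". SAP 2.9 gives the strata for it: "Descriptive summary statistics will be provided by Age group/formulation at each scheduled time point". Protocol 12.5.3 uses the same strata; the protocol's wording is "Descriptive summary statistics will be provided by age group/formulation at each scheduled time point".

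SAP 2.2 deals with children whose starting dose is below the assigned level because of a CYP inhibitor: "these subjects will be included under the assigned dose level and considered that they have received the full assigned dose". It then sets the reach of that rule: "This applies to Full Analysis Set, Safety Set, and Pharmacokinetic analysis set as described below". Protocol section 12 has the same rule.

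For a concentration to be evaluable, SAP 2.2 asks that a dose was taken beforehand, that there was no vomiting within two hours, and that a pre-dose sample preceded the next dose. Neither the amount taken nor inhibitor use is a criterion. SAP Table 2-3 excludes starting doses that are off the age-based schedule (TRT01/TRT02) from the PK set.

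On dosing with inhibitors, Protocol 6.5.1.3 says: "A dose reduction of ruxolitinib (e.g. by 50%) should be considered when using strong CYP3A4 inhibitors". For safety reductions, Protocol Table 6-4 gives one step for Group 2 as "5 mg QD or 2.5mg BID". Protocol 6.1.1 allows safety dose changes before Cycle 7 Day 1. Protocol 8.5.1.1 takes post-dose samples on Day 1 in the first five children of each of Groups 1 to 3, and pre-dose samples in all children up to Cycle 7 Day 1.

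**The concern.** Counting a CYP-reduced starter at the assigned dose is a sensible convention for efficacy and safety, where the question is about a treatment policy. A concentration is a measurement that depends directly on the dose taken, the interval since that dose, and clearance.

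Under the plan, one table cell can hold samples at the assigned dose without inhibitor, at a reduced dose with inhibitor, at the full dose with inhibitor (the reduction need only be considered), and at a dose or frequency reduced for toxicity. Day 1 post-dose cells are exposed only to the first three kinds. Pre-dose cells from Cycle 1 Day 8 onward are exposed to all four.

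The situation is foreseeable. Protocol 6.2.1.1 names azole prophylaxis among usual concomitant drugs, and Table 16-8 lists itraconazole, posaconazole and voriconazole as strong CYP3A inhibitors and fluconazole as a dual inhibitor. The plan is also uneven: it excludes off-schedule starting doses from the PK set and flags formulation changes, but has no flag for reduced dose or inhibitor use. At stake are the means, CV% and profiles reported for a secondary endpoint.

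**Working it through.** There is no planned figure to reproduce, so this is an illustration of size.

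**Inputs from the protocol.** Half-life 2.3 h (paediatric) and about 3 h (adult), and linear PK, all from 1.1.2.1.2; 12-hourly dosing; post-dose samples at 0.5, 2 and 6 h (Table 8-6).

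**Assumptions.** One compartment; volume and bioavailability unchanged by the inhibitor; the inhibitor divides clearance by f, with f = 2 as the central case (suggested by the 50% dose reduction) and 1.5 to 2.5 as the range; absorption rate ka of 2 to 4 per hour.

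**AUC.** The ratio of half dose plus inhibitor to full dose without is 0.5 × f: 0.75, 1.00 and 1.25 for f = 1.5, 2 and 2.5.

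**Trough, bolus form.** Trough ∝ D·e^(−kτ)/(1 − e^(−kτ)), with k = ln 2 / half-life, τ = 12 h and f = 2.
- Half-life 3 h: assigned dose 0.0625/0.9375 = 0.0667. Half dose with a 6 h half-life: 0.5 × 0.25/0.75 = 0.1667. Ratio 2.50.
- Half-life 2.3 h: assigned dose 0.0269/0.9731 = 0.0276. Half dose with a 4.6 h half-life: 0.5 × 0.1640/0.8360 = 0.0981. Ratio 3.55.

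**Oral form.** C(t) ∝ D·ka/(ka − k)·(e^(−kt) − e^(−ka·t)); at steady state each exponential is divided by one minus its own value at 12 h. The ranges below span both half-lives and both ka values.

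| f | 0.5 h | 2 h | 6 h | steady-state trough |
|---|---|---|---|---|
| 1.5 | 0.51–0.52 | 0.56–0.60 | 0.76–0.89 | 1.34–1.74 |
| 2 | 0.52–0.53 | 0.59–0.65 | 0.94–1.19 | 2.35–3.41 |
| 2.5 | 0.52–0.53 | 0.62–0.68 | 1.07–1.41 | 3.42–5.31 |

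Taking both forms together at f = 2, the trough ratio is 2.35 to 3.55. At 0.5 h the bolus form gives 0.53 to 0.54, so the joint range is 0.52 to 0.54. A child on the full dose with inhibitor has twice the half-dose trough: 4.7 to 7.1.

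**Effect on a cell mean, one affected child, f = 2.**
- Five children, 0.5 h: (4 + 0.52)/5 = 0.904 to (4 + 0.54)/5 = 0.908, about −9% to −10%.
- Five children, trough: (4 + 2.35)/5 = 1.27 to (4 + 3.55)/5 = 1.51, so +27% to +51%. The geometric mean moves less: 2.35^0.2 = 1.19 to 3.55^0.2 = 1.29.
- Larger trough cells: Amendment 2 reports 22, 17 and 7 children enrolled in Groups 1 to 3. Before any formulation split, one child in 7 gives (6 + 2.35)/7 = 1.19 to (6 + 3.55)/7 = 1.36; one in 22 gives (21 + 2.35)/22 = 1.06 to (21 + 3.55)/22 = 1.12.

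**Safety reductions without inhibitor.** Half the dose at the same frequency gives 0.5, so one in five lowers the mean by 10%. A change to once daily, sampled 24 h after the last dose, is more extreme. In the bolus form, 5 mg QD against 5 mg BID in Group 2 gives a trough ratio of 0.059 (3 h half-life) or 0.026 (2.3 h).

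**The case against.** The strongest reply is that age group already is the assigned-dose stratum. Dose is allocated by age (Protocol 6.3.2), and SAP 2.4.1 shows one planned daily dose per enrolled group: 20 mg, 10 mg and 8 mg/m², each twice the BID dose. Off-schedule starters are excluded. A reader might infer that the endpoint describes no assigned dose at all; the documents do not support that. Samples from children on the assigned dose without inhibitor are valid and sit in the right stratum.

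A reader might also infer that these tables were to confirm the age-based doses. Protocol sections 3 and 4.2 give that task, for children under 12, mainly to the paediatric acute GvHD study.

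Formulation gives some separation. The 5 mg tablet cannot be broken (Table 6-1), so 2.5 mg BID needs the liquid. A formulation switch before Cycle 7 Day 1 needs sponsor approval, and SAP 2.2 flags it for possible use in PK analyses. That child is still counted under the starting formulation, however, and a 5 mg QD tablet child shares a cell with 5 mg BID tablet children.

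Population PK is planned separately and may model dose and inhibitors. Its plan is not available, SAP 2.9 says parameters may be derived where the protocol says they will be, and it would not alter the CSR concentration tables. Listings of concentrations and doses let a diligent reader trace affected children, but leave the summaries mixed. The by-dose rule in SAP 2.4.1 covers study-treatment summaries and is triggered by assigned dose, so it does not close the gap.

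**Conclusion.** The concern holds in limited form. The concentration summaries are stratified by assignment and formulation, while actual dose, frequency and inhibitor use vary within cells, and SAP 2.2 labels a known reduced start as full dose for PK. AUC may be little changed at half dose with an inhibitor, but the endpoint is concentration at each time point.

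At halved clearance the trough ratio is 2.35 to 3.55; for a 1.5- to 2.5-fold fall in clearance it is about 1.3 to 5.3. The size therefore rests on an assumed inhibitor effect and a simple model. The documents do not say how many children used inhibitors or had reductions, so the actual distortion of any table cannot be computed. It could be negligible in a large cell with no affected child, and material in the five-child post-dose cells or in Group 3. No view is taken here on which dosing rule is right.

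**What to change.** Keep these children in the PK analysis set. In SAP 2.2, add that the full-dose convention does not determine how individual concentrations are classified in PK summaries. Simply removing the PK set from the rule would be worse: it would not touch later safety reductions, and it could expose CYP-reduced starters to exclusion under TRT01/TRT02.

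In SAP 2.9:
- flag each concentration by actual dose and frequency at sampling, and by use of a strong CYP3A4 or dual CYP3A4/CYP2C9 inhibitor;
- add a summary table and profile limited to samples at the assigned dose and frequency without such an inhibitor;
- show the other samples separately, by listing where cells are very small.

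The dosing and concomitant-medication eCRFs already collect what is needed. The cost is SAP wording and one supplementary set of tables and figures, since SAP 2.9 does not otherwise repeat PK for the final CSR. The drawback is small cells, especially in Group 3 with seven children enrolled. The output should be labelled supplementary, as it would be specified after the interim PK summaries.

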2.10 PD and PK/PD analyses

Analyses of PK data will not be repeated for the final CSR.

Exposure-Response analysis

A detailed description of exposure-response analysis may be developed in an independent analysis plan if the data permits, and the analysis will be documented in a separate report. Briefly, the objectives are to:

- Characterize the exposure-efficacy relationship of ruxolitinib in terms of concentration-effect and dose-effect (effect: overall response rate at Cycle 7 Day 1; Overall survival at Cycle 4 Day 1, Cycle 7 Day 1 and 12 months). Exposure metrics will be described in further detail in the analysis plan.
- Characterize the exposure-safety relationship of ruxolitinib in terms of concentration-AEs and/or dose-AEs (AEs: frequency of AEs, severity of AEs, AEs of special interest, time to onset of AEs). Exposure metrics will be described in further details in the analysis plan
- Explore exposure-biomarker relationships as appropriate – immune cell subsets, inflammatory cytokine levels and soluble cGvHD biomarkers.

